## ABBREVIATIONS

AE / SAE	Adverse Event / Serious Adverse Event
ALS	Amyotrophic Lateral Sclerosis
ALT	Alanine Transaminase (SGPT)
ALSFRS-R	Revised Amyotrophic Lateral Sclerosis Functional Rating Scale
Anti-HCV	Hepatitis C antibodies
AST	Aspartate Transaminase (SGOT)
cDNA	Complementary Deoxyribonucleic Acid
CFR	Code of Federal Regulation
CLI	Critical Limb Ischemia
cm	Centimeter(s)
CRF	Case Report Form
CRO	Clinical Research Organization
Cu/Zn	Copper/Zinc
DNA	Deoxyribonucleic Acid
DSMB	Data Safety Monitoring Board
EAAT2	Excitatory amino acid transporter 2
EKG	Electrocardiogram
ER	Endoplasmic Reticulum
FDA	Food and Drug Administration
GDNF	Glial cell line-derived neurotrophic factor
HBV	Hepatitis B Virus
HBcAb	Hepatitis B core antibody
HBsAb	Antibody to Hepatitis B surface antigen (IgG and IgM)
HBsAg	Hepatitis B surface antigen
HCV	Hepatitis C Virus
HGF	Hepatocyte Growth Factor
HIV	Human Immunodeficiency Virus
HTLV	Anti-Human T-Cell Lymphotropic Virus
IND	Investigational New Drug
LLOQ	Lower limit of quantitation
MCP-1	Monocyte chemoattractant protein 1
NGF	Nerve growth factor
NMDA	N-Methyl-D-aspartate
NO	Nitric Oxide
PGE2	Prostaglandin E2
RNA	Ribonucleic Acid
ROS	Reactive oxygen species
SBP	Systolic Blood Pressure
SGPT	Serum Glutamic Pyruvic Transaminase (same as ALT)
TAF	Treatment Authorization Form
TNF	Tumor necrosis factor
SOP	Standard Operating Procedure
VEGF	Vascular endothelial growth factor
WBC	White Blood Cell Count
WFI	Water for Injection

---

## 1. AMYOTROPHIC LATERAL SCLEROSIS

---

Amyotrophic Lateral Sclerosis (ALS) is an adult-onset neurodegenerative disorder characterized by the loss of upper and lower motor neurons. The disease is diverse in its presentation, cause, and progression, but, in general, ALS presents clinically as asymmetric muscle weakness, wasting, spasticity, weight loss, and paralysis. Pathologically, ALS is characterized by progressive degeneration and loss of motor neurons in the spinal cord, brainstem, and cerebral cortex. Death usually occurs within 2–5 years of symptoms onset, most commonly due to respiratory failure. While the majority of ALS cases are sporadic (primary or idiopathic), about 5 – 10% of patients have a positive family history (familial ALS), with a mutation in the Cu/Zn superoxide dismutase 1 (*SOD1*) gene accounting for 10% of familial ALS.

The incidence of ALS is 1-2 per 100,000 people. It is estimated that as many as 30,000 Americans may have the disease at any given time, but less than 6,000 are diagnosed annually. There is no effective treatment for ALS. The only drug currently approved by FDA for the treatment of this disease is a glutamate release inhibitor (Rilutek, generic: riluzole), which also interferes with N-methyl-D-aspartate (NMDA) receptor mediated events. Its effect is both minimal and controversial.

### 1.1. PATHOPHYSIOLOGY

---

Multiple mechanisms for the selective vulnerability, degeneration and early dying-back axonopathy of motor neurons have been proposed and investigated. They include: protein misfolding, mitochondrial dysfunction, oxidative damage, defective axonal transport, excitotoxicity, insufficient growth factor signaling, and inflammation. Toxicity results from a combination of damage incurred directly within motor neurons and through damage incurred by nonneuronal neighbors, including astrocytes and microglia, whose actions amplify the initial damage and drive disease progression and spread. Microglia activate an inflammatory cascade via secretion of monocyte chemoattractant protein 1 (MCP-1) and other cytokines. Astrocytes contribute to neuron injury by releasing inflammatory mediators such as nitric oxide (NO) and PGE2, reduced lactate release, activation of pro-NGF-p75 (nerve growth factor) receptor signaling and reduced activity of the glutamate reuptake transporter excitatory amino acid transporter 2 (EAAT2). Motor neurons might also undergo transcriptional dysregulation and abnormal RNA processing which, together with overproduction of reactive oxygen species (ROS), contribute to aberrant protein folding. Aberrant proteins can form aggregates, leading to proteasome impairment and endoplasmic reticulum (ER) stress. The resulting mitochondrial impairment and dysregulation of calcium handling trigger autophagy and the apoptotic cascade. The process is ‘contagious’ and self-perpetuating, affecting the dynamics of cell death in neighboring cells due to release of interleukin-1 $\beta$ , TNF- $\alpha$ , and free radicals. [Figure 1](#) depicts the molecular processes involved in motor neuron injury in ALS.

[figure not shown]

Figure 1. Molecular mechanisms of motor neuron injury in ALS  
from: Ferraiuolo, L., J. Kirby, et al. (2011)

***The caspase family.*** Regardless of the underlying metabolic pathway to degeneration, the end result in ALS is motor neuron death. The major executioners in the apoptotic process are proteases known as caspases (cysteine-dependent, aspartate-specific proteases). Caspases directly and indirectly orchestrate the morphologic changes of the cell during apoptosis. They exist as latent precursors, which, when activated, initiate the death program by destroying key components of the cellular infrastructure and activating factors that mediate damage to the cells.

The first evidence of the role of caspases in a neurodegenerative disease came from experiments in which the “ALS mouse” (SODG93A) was cross-bred with a mouse expressing a mutant caspase 1 gene that inhibited caspase 1 in neurons. Mice expressing the mutant SOD1 transgene *and* the mutant caspase 1 transgene survived 9% longer, and disease progression was slowed by more than 50 percent. Caspase inhibition in the same model was found to be neuroprotective and extended survival by 22%.

The clinical relevance of these studies is supported by findings in ALS patients. Early activation of caspase-1 in ALS contributes significantly to toxicity. However, neuronal death only occurs following upregulation and concomitant expression of

---

caspase-3. A therapy that could block the upregulation of caspases could potentially improve survival and quality of life of ALS patients.

---

## **1.2. CURRENT TREATMENT OPTIONS**

---

Rilutek, (originally manufactured by Sanofi Aventis and approved as an orphan drug on December 12, 1995 (NDA 020599)), is now off-patent and available in the generic form of riluzole. Rilutek was approved on the basis of two controlled trials in which the time to tracheostomy or death was longer for patients randomized to Rilutek than for those randomized to placebo. These studies admitted patients with either familial or sporadic ALS, disease duration of less than 5 years, and a baseline forced vital capacity greater than or equal to 60%. In one study, performed in France and Belgium, 155 ALS patients were followed for at least 13 months (maximum duration 18 months) after being randomized to either 100 mg/day (given 50 mg BID) of Rilutek or placebo. The second study was conducted in both Europe and North America. 959 ALS patients were followed for at least 1 year (North American centers) and up to 18 months (European centers) after being randomized to either 50, 100, 200 mg/day of Rilutek or placebo. The studies concluded that Rilutek extends early survival and / or time to tracheostomy, but there was no statistically significant difference in mortality at the end of the studies.

---

## **1.3. UNMET CLINICAL NEED**

---

Riluzole does not prevent or correct the underlying causes of ALS. It has not been shown to improve muscle strength or neurological function. Clearly, a therapy that could impede or reverse neurodegeneration is needed for patients with ALS.

---

## **1.4. HGF FOR THE TREATMENT OF AMYOTROPHIC LATERAL SCLEROSIS**

---

Hepatocyte growth factor (HGF) is a multi-functional mesenchyme-derived cytokine. It is a recognized potent angiogenic growth factor and anti-apoptosis agent, stimulating the growth of endothelial cells and the migration of vascular smooth muscle cells. HGF stimulates DNA, RNA and protein synthesis by endothelial cells in a dose-dependent manner, upregulates vascular endothelial growth factor (VEGF) expression, and exhibits greater mitogenic activity than that of VEGF alone in human aortic endothelial cells *in vitro*.

Although largely thought of as an angiogenic agent, HGF has been recently identified as a neurotrophic factor. HGF and its cognate receptor (the c-Met receptor) are expressed in the peripheral nervous system as well as in various regions of the brain and spinal cord. W. Sun, *et al.* (2002) found that local sustained HGF production in neural tissue in SODG93A mice (transgenic ALS model) alleviated the symptoms of ALS by direct neurotrophic activities on motor neurons and indirect activities on glial cells. It suppresses microgliosis and astrogliosis, which contribute to motor neuron degeneration by producing cytotoxic cytokines and eventual glial scar formation.

Early in the disease, surviving nerve fibers establish connections and reinnervate motor units (muscle groups) that have lost their connection to axons that have died. As a result, larger motor units are formed. HGF may be able to slow disease progress by facilitating reinnervation. It has been demonstrated that HGF can promote neurogenesis, angiogenesis, and synaptogenesis and that it can inhibit fibrotic changes in ischemic regions better than glial cell line-derived neurotrophic factor (GDNF).

HGF may also have protective effects against excitotoxic injuries, because it has been shown to attenuate axonal degeneration by reducing over-excitation (excitotoxicity) through modulation of the expression of the scaffolding protein of the NMDA receptor at the synapse.

Finally, HGF may stave off cell death and halt the cascade of neighboring cell damage by inhibiting caspase signaling. In ALS patients, chronic, sublethal activation of caspase appears to mediate cell dysfunction, which precedes cell death. Cell dysfunction of substantial magnitude, occurring before cell death, might result in symptomatic disease. Given that caspases may be active in individual neurons for a long period (potentially weeks to months), inhibition of caspase in these circumstances could reduce cell dysfunction and delay cell death.

Figure 2 depicts the action of HGF on motor neurons. HGF binds to c-Met on cell surface and induces autophosphorylation of the intracellular tyrosine residues of c-Met. Subsequently, HGF inhibits caspase-1 activation, induces XIAP and inhibits its downstream caspases, caspase-3, -7 and -9, thereby effectively dampening caspase-dependent cascades. Therefore, the neurotrophic action of HGF on motor neurons is, at least in part, promoted by preventing caspase-mediated cell death signals.

[figure not shown]

Figure 2. Molecular mechanisms of the neuroprotective effects of HGF  
*from: Kadoyama, K., H. Funakoshi, et al. (2007)*

---

The challenge associated with delivering a targeted sustained dose of exogenous HGF is in overcoming the instability of HGF in blood circulation and its rapid clearance by the liver; HGF has an *in vivo* half-life of less than 15 minutes.

One approach to increasing HGF available to neurons is to develop a gene transfer strategy that would allow for persistent expression of HGF protein *in vivo*. Although plasmid DNA is one of the least efficient gene transfer systems currently in use, the fact that it is associated with limited persistence and no propensity for genomic integration, (particularly in skeletal muscle tissue) makes it an attractive option for local targeted delivery.

[figure not shown]
---

### 1.5. VM202

---

[REDACTED]

[REDACTED]

**Safety of VM202.** The use of plasmids for targeted delivery of angiogenic factors into muscle tissue is a particularly attractive and a relatively safe therapeutic approach, because plasmids have been shown to effectively transfect postmitotic cells such as skeletal and heart muscle and to successfully express angiogenic genes with very little dissemination and persistence at distant sites. Following intramuscular injection, the plasmid that persists is extrachromosomal and integration into host DNA, if it occurs, is negligible. This local effect of conventionally injected naked plasmid DNA is well known.

---

**Potential Efficacy of VM202.** VM202 has demonstrated potential for stimulating angiogenesis in animal models. Its ability to transfect skeletal muscle and produce HGF locally at the site of injection may help support nerve health, regeneration and to forestall motor neuron die-off.

---

**1.6. PRECLINICAL DATA**

---

The non-clinical safety of VM202 has been evaluated for general toxicity following single intramuscular and intravenous doses in rats. In addition, the general toxicity of VM202 following multiple intermittent (weekly or monthly) intramuscular doses has been evaluated in rabbits and rats, respectively. The potential for genomic integration at the injection site as well as the potential for distribution to and persistence of VM202 in reproductive tissues was evaluated in rats. The ability of VM202 to induce humoral immune responses was evaluated following intramuscular administration with or without adjuvant in mice. All species utilized for these studies (mouse, rat, and rabbit) were shown in *in vivo* experiments to be able to express the plasmid following intramuscular injection.

[REDACTED]

[REDACTED]

Therefore, the nonclinical efficacy and safety studies support the clinical investigation of VM202 in subjects with amyotrophic lateral sclerosis.

---

**1.7. CLINICAL DATA**

---

VM202 was/is being evaluated in four clinical trials.

**1.7.1. PHASE I STUDY IN CRITICAL LIMB ISCHEMIA**

---

[REDACTED]

---

[REDACTED]

[REDACTED]

Median ABI and TBI significantly increased from 0.35 to 0.52 ( $P=0.005$ ) and 0.15 to 0.24 ( $P=0.01$ ) at 12 months follow-up. TCPO2 showed an improvement trend (increase). A significant reduction in pain was reported by nine of eleven subjects, with median VAS decreasing from 58 to 16 ( $P=0.03$ ) at 6 months follow-up. VAS score reduction tracked well with the hemodynamic data.

In general, there was more improvement over baseline in Cohort II (4 mg VM202) than in any other cohort. Cohort I (2 mg of VM202) also experienced a significant reduction in pain and modest improvement in hemodynamic measurement. Interestingly, 2 subjects in each of these cohorts had diabetes, possibly suggesting some benefit of VM202 in this subpopulation. Doses of aspirin above 81 mg daily may have an inhibitory effect on the therapeutic activity of VM202. Results from this study have been published in *Gene Therapy* in 2011.

### 1.7.2. PHASE II STUDY IN CRITICAL LIMB ISCHEMIA

[REDACTED]

[REDACTED]

---

[REDACTED]

[REDACTED]

[REDACTED]

[REDACTED]

[REDACTED]

**1.7.3. PHASE I/II STUDY IN PATIENTS WITH PAINFUL DPN**

[REDACTED]

[REDACTED]

[REDACTED]

---

[REDACTED]

[REDACTED]

#### 1.7.4. PHASE II STUDY IN PATIENTS WITH PAINFUL DPN

[REDACTED]

[REDACTED]

[REDACTED]

***Preliminary Conclusions.*** These early data support the feasibility and safety of intramuscular injections of VM202 in subjects with critical limb ischemia and DPN. Results suggest that this therapeutic approach may improve functional outcomes and provide symptomatic relief. VM202 is rapidly eliminated from circulation, and appears to remain active only at the injection site. Considering the potential benefit of targeted delivery of HGF to motor neurons in patients with ALS, study of VM202 in this population is warranted.

---

## **1.8. STUDY AND DOSE RATIONALE**

The natural history of ALS is characterized by unremitting deterioration of neuromotor function. Deterioration rates and patterns vary, with death occurring as rapidly as 1–2 years, but more commonly, within 3-5 years of initial diagnosis. For the majority of patients, symptoms begin with limb involvement. Symptoms may first manifest in the upper or lower limbs first, but regardless of the order in which muscle wasting occurs, the disease is progressive, self-perpetuating, and ultimately results in significant atrophy and weakness in all limbs. We therefore propose treating both upper and lower limbs.

The proposed final (cumulative) dose to be administered to each subject is 64 mg VM202. A dosing schedule similar to the one used in the phase I and the phase II DPN studies will be used in this study. Namely, intramuscular injections for each target muscle group will be divided into two injection visits, (equal halves), two weeks apart. As in all four prior studies, VM202 will be delivered in a solution of 0.5 mg VM202 / mL. The proposed dose is well within that supported by the body of pharmacology and toxicology safety studies of VM202. Safety studies in rabbit, rat and mouse models demonstrate that doses of up to approximately 12.8 times the cumulative clinical dose proposed in this study are safe and resulted in no toxicities. The dose to each muscle group (VM202 is only active once transfected into skeletal muscle cells) falls within the doses given in the four other clinical studies. The excellent safety profile of VM202 seen thus far in the phase I and phase II CLI studies, the phase I/II study in patients with DPN, and from the ongoing phase II DPN study supports this dosing scheme.

---

## **2. GOOD CLINICAL PRACTICES (GCP) STATEMENT**

This trial will be conducted in compliance with all applicable federal regulations pertaining to investigational drugs and devices including but not limited to: 21 CFR Part 50, Part 54, Part 56, Part 312, and GCP standards. This trial will be conducted in compliance with the protocol as approved by the Institutional Review Board (IRB) and the Institutional Biosafety Committee (IBC) at the study site. Any deviations from the protocol that may affect the safety and welfare of study participants will be immediately reported to the Sponsor and to the IRB and IBC per the institution's guidelines.

---

## **3. INVESTIGATIONAL PLAN**

### **3.1. STUDY OBJECTIVES**

The objective of this Phase I/II study is to evaluate the safety and tolerability of IM administration of VM202 at different injection sites in subjects with ALS.

---

---

### 3.2. STUDY DESIGN

This is a phase I/II, open label, single center study designed to assess the safety and tolerability of intramuscular injections of VM202 in patients with ALS. Subjects with ALS will be screened for study eligibility after giving informed consent.

**Screening.** Using the revised El Escorial / Airlie House diagnostic criteria and medical history, subjects will be confirmed as having ALS < 2 years. If applicable, the subject will be washed out of prohibited medication (see [section 3.4.4](#)). During medication wash-out, screening procedures consisting of assessment of study eligibility, a medical history, vital signs, physical exam, concomitant medications, ALSFRS-R, viral screening, 12 lead EKG, FVC, serum chemistry and hematology, and (urine) pregnancy test (for women of childbearing potential only) will be performed.

All screening assessments should occur within the 30 days prior to Day 0 (day of first injections).

**Injection.** Prior to injections on Day 0, subjects will be assessed using the ALSFRS-R, the Medical Research Council (MRC) scale for muscle strength testing, dynamometry, FVC, and muscle circumference. These tests can be conducted one day before the scheduled injection visit. Immediately before injection on Day 0, the following will be conducted: recording of concomitant medications, vital signs, and blood draw for serum chemistry and hematology, serum HGF and copies of VM202 in whole blood.

VM202 will be delivered in 0.5 mL intramuscular injections of a solution of 0.5 mg VM202 / mL. It will be administered over the course of four visits: Day 0, Day 7, Day 14, and Day 21. As in all previous VM202 studies, final dose of VM202 for each target muscle group is divided and administered 2 weeks apart. However, in order to reduce the injection burden on the ALS patient, injection of the upper limbs will be done on separate visits from injection of the lower limbs. The first eligible subject will begin with the lower limb injection series and will be injected in accordance with the schedule outlined in [Table 3](#). The next sequentially eligible patient will begin with injection of the upper limbs (see [Table 4](#)). Subsequent eligible patients will be treated in an alternating fashion, such that 9 patients will have initiated their VM202 injections in the lower limbs and 9 patients will have initiated their VM202 injections in the upper limbs. ***Please note: Regardless of injection order, all subjects will receive the same final dose of VM202 and the same number of injections per muscle group.***

---

[REDACTED]

[REDACTED]

Serum chemistry and hematology will be determined on Day 0, Day 30, Day 90 and 9 months.

FVC, ALSFRS-R, and muscle strength (MRC scale) will be assessed at Day 0, Day 30, Day 60, Day 90, at 6 months and 9 months. Muscle circumference and dynamometry will be ascertained on Day 0, Day 60, Day 90, at 6 months, and 9 months.

Concomitant medications and vital signs will be recorded throughout the 9 month follow-up period. Adverse events will be assessed starting on Day 0 throughout the 9 month follow-up period, and injection site reactions will be assessed starting on Day 0 through Day 60. Study enrollment will be staged. Enrollment will be halted after the sixth subject qualifies for treatment. A Data Safety Monitoring Board (DSMB) will conduct a safety evaluation after the first patient treated completes the Day 60 follow-up evaluation and the five other sequentially enrolled subjects complete at least the Day 30 follow-up. Enrollment will be suspended until a formal recommendation to proceed (or not proceed) is made by the DSMB.

The study will be suspended pending DSMB review if any of the following SAEs are attributed to VM202 injections during any time during the study:

- acute anaphylaxis (including erythema, hives, wheezing, stridor or respiratory distress);
- temperature >102°F with negative blood cultures within 24 hours of study drug administration; or
- evidence of active tissue necrosis at the injection site within two weeks of study drug administration.

A summary of the schedule of evaluations and study visits can be found in [Appendix 1](#).

---

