#### **3.5.2. DISCONTINUED SUBJECTS**

---

Any subject may voluntarily discontinue the study at any time without prejudice. The Investigator may discontinue a subject from the study at any time if (s)he considers that remaining in the study compromises the subject's health or the subject is not sufficiently cooperative. In either event, reason(s) for discontinuation should be recorded on the CRF.

Possible reasons for study discontinuation include the following:

- Adverse events (AEs) necessitating discontinuation from the study (pre-treatment)
- The subject is lost to follow-up
- Subject decision
- Investigator decision
- Other reason

The reasons for any subject discontinuation will be specified and recorded on the study completion form of the CRF. Additional subjects may be enrolled if subjects discontinue prior to the 90 day visit.

Subjects discontinued for AE(s) will be followed-up after subject's discontinuation until the event is resolved or considered medically stable by the Investigator.

Subjects that withdraw prior to study completion will undergo the following assessments if possible:

- 
1. Concomitant Medications
  2. Vital signs
  3. Physical exam

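### Section 3.2 suspends the study automatically for three attributed reactions only; an attributed death or life-threatening SAE of any other kind forces no pause in dosing or enrollment

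*Combined protocol and SAP*

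**What the plan says.** Section 3.1 sets the purpose of the trial: "The objective of this Phase I/II study is to evaluate the safety and tolerability of IM administration of VM202". Section 3.2 describes the design: "This is a phase I/II, open label, single center study".

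The suspension rule is in Section 3.2: "The study will be suspended pending DSMB review if any of the following SAEs are attributed to VM202 injections". It applies at any time in the study and lists three items. The first is acute anaphylaxis, with skin and airway signs given as inclusions. The second is "temperature >102°F with negative blood cultures within 24 hours of study drug administration; or". The third and last is "evidence of active tissue necrosis at the injection site within two weeks of study drug administration".

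Section 3.2 also stages enrollment. Entry stops once the sixth subject qualifies. The DSMB then makes a safety evaluation when the first treated subject has completed Day 60 and "the five other sequentially enrolled subjects complete at least the Day 30 follow-up". After that, "Enrollment will be suspended until a formal recommendation to proceed (or not proceed) is made by the DSMB".

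Section 5.1 counts death and life-threatening events as SAEs. Neither is named as such in the suspension list.

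**The concern.** The rule ranks events in an odd order. An attributed SAE of culture-negative fever above 102°F within 24 hours stops the study until the board has looked. An attributed death from a cause outside the list does not.

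Such cases are easy to construct. Each visit involves 52 or 76 injections (Tables 1 and 2). A fatal bloodstream infection attributed to them, with positive cultures, fails the second item by its own wording. Life-threatening necrosis that appears after two weeks fails the third.

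What is at stake is that other subjects could be injected, or new ones enrolled, before anyone is obliged to stop. In a trial whose stated objective is safety and tolerability, the gravest attributed events should carry at least the pause that the three listed reactions carry.

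**Working it through.** **1. Is the list closed?** The connective before the third item marks it as the last, and no catch-all follows. The blacked-out blocks in Section 3.2 come before the laboratory schedule, not inside the list.

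**2. Does any other provision require a pause?**

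| Provision | What it does | Requires a pause? |
|---|---|---|
| Synopsis, other study procedures | DSMB monitors safety for the whole study | No |
| 3.2, staged enrollment | One DSMB evaluation, timed by follow-up of the first six | Holds enrollment after the sixth subject; does not interrupt dosing under way |
| 3.5.2 | "The Investigator may discontinue a subject from the study at any time" if health is compromised | No; discretionary, one subject |
| 3.5.3 | Sponsor may end the study | No; discretionary |
| 5.4.1 | SAEs to Sponsor and CRO within 72 hours; IRB and IBC as applicable | No |
| 5.4.2 | Unexpected fatal or life-threatening AEs to FDA in 7 days; Investigators told of safety information that bears on conduct | No |
| 9 and 10 | IRB and IBC notified as they require | No |
| 13 | Emergency changes allowed to remove an immediate hazard | No; permissive |

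**3. When does the staged evaluation fall?** The fourth injection is on Day 21 ± 1, so at the latest Day 21 + 1 = Day 22. The Day 30 visit has a window of ± 3 days, so at the earliest Day 30 − 3 = Day 27. The evaluation therefore follows all planned dosing of the first six and precedes dosing of the other 12. It interrupts dosing in neither group.

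**4. Planned exposure.** Inputs: 18 subjects (Section 3.3); four injection visits, 256 injections and 64 mg per subject (Tables 1 and 2).

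- All subjects: 18 × 4 = 72 visits.
- First six: 6 × 4 = 24 visits; 24/72 = 33%.
- Other 12: 12 × 4 = 48 visits; 48/72 = 67%; 12 × 256 = 3,072 injections; 12 × 64 = 768 mg.

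**5. Example: the event occurs in subject 10.**

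- Subjects 11–18: 8 × 4 = 32 planned visits; 32/72 = 44%; 8 × 256 = 2,048 injections; 8 × 64 = 512 mg. Between 0 and 32 of these visits still lie ahead, depending on accrual and on the timing of the event.
- Subjects 7–9 could also be in mid-course. Their planned total is 3 × 4 = 12 visits, and an unknown part of it could remain. The ceiling for all these subjects is 32 + 12 = 44 visits (44/72 = 61%); the floor is 0.

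The plan states no figure of its own on this point, so there is none to reproduce.

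**The case against.** The best case for the plan is that a small, single-site, open-label trial does not need a rule for this. The Investigator who treats the subjects also judges causality, would know of a death at once, and may withdraw subjects. The Sponsor can stop the study, and FDA, IRB and IBC hear of the event as required. The three listed items are the acute and local reactions one would look for after injecting a plasmid. The first is broad enough, since it mentions respiratory distress, to catch some acute respiratory events. ALS is itself fatal, so a trigger set at the level where causality cannot be excluded could halt dosing for a death due to the disease.

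Much of this stands. It makes continued dosing after an obviously related death unlikely. But each of these routes is discretionary or only informs someone. The protocol already chose not to rely on discretion for three less grave events.

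A reader might go further and infer that such an event requires no DSMB review at all, or that there is no route by which it reaches the board. The documents do not support that. The synopsis gives the DSMB a duty to monitor safety throughout. An event among the first six would ordinarily come before the mandatory staged evaluation. A DSMB charter, which is not among the documents, may set how events reach the board. The point is confined to the missing automatic pause.

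**Conclusion.** The concern holds in that form. As written, Section 3.2 forces suspension for three attributed SAEs. It forces none for an attributed death or life-threatening SAE outside them, and no other section supplies the pause. A fatal case of a listed reaction, such as fatal anaphylaxis, is already covered.

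The gap differs by stage. In the first six subjects, entry of the seventh is held in any case. What is missing there is a stop to entry of the remaining first-six subjects and to injections under way. After the staged evaluation, which leaves 48 of the 72 planned visits, neither dosing nor enrollment has an automatic stop for such an event.

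These counts are planned exposure. They assume 18 subjects, no replacements (Section 3.5.2 allows them for discontinuation before Day 90) and visits within window. They say nothing about how likely such an event is. This is a design choice worth changing rather than an error of analysis, held with medium confidence because the charter has not been seen.

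**What to change.** Add a fourth item to the Section 3.2 list: any death or life-threatening SAE attributed to VM202 or the injection procedure.

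State one causality threshold for all four items, because the present wording does not say which grades of the four-level scale in Section 5.2.1 count as attributed. At least possibly related is suggested. It agrees with Section 5.4.2, which treats possibly related events as suspected adverse reactions.

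State that dosing and enrollment of all subjects pause until the DSMB has reviewed the event. Once all planned injections have been given there is nothing to pause, and the item then prompts DSMB review only.

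The cost in text is one list item and a few sentences, using a board that already exists. The cost in conduct is that an ambiguous ALS-related death soon after dosing could cause a short pause. This is limited because Section 5.1 does not count changes consistent with natural progression as AEs. A pause could also push a subject in mid-course outside the ± 1 day injection window, as the three existing triggers already can.
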